# Study Protocol with Statistical Analysis Plan and Informed Consent Form

## Detailed Description:

Persistent olfactory dysfunction (OD) is a common sequela of viral upper respiratory tract infections, including COVID-19, and can significantly affect patients' quality of life, nutrition, and safety. Current treatment options are limited, with olfactory training being the primary evidence-based non-pharmacological therapy. Autologous platelet-rich plasma (PRP) is a concentration of platelets obtained from a patient's own blood, rich in growth factors and cytokines that promote neuronal regeneration, tissue repair, and neuroplasticity. Early clinical studies suggest PRP may improve olfactory function, but the optimal method for delivering PRP to the olfactory cleft remains unknown.

This single-blind, randomized controlled trial will include a total of 60 adult patients aged 18-80 years old with olfactory loss (hyposmia or anosmia) persisting for more than 3 months despite standardized olfactory training, confirmed by a reduced Sniffin' Sticks TDI score.

PRP will be prepared on-site immediately before application using a standardized centrifugation protocol to achieve a platelet concentration 2-3 times above baseline. Efficacy and safety of two PRP delivery methods will be compared:

- (1) *Intranasal Injection Group*: Autologous PRP will be injected directly into the mucosa of the olfactory cleft under endoscopic guidance. After topical anesthesia with lidocaine spray and decongestion with oxymetazoline, a 25-gauge needle will be used to deliver approximately 1 mL of PRP into multiple sites along the superior nasal cavity bilaterally.
- (2) *Carrier-Assisted Topical Application Group*: Four pieces of sterile, bioabsorbable carrier (Gelfoam sponge) will be soaked with approximately 5 mL of autologous PRP. Under endoscopic guidance, two pieces of PRP-soaked carrier will be placed gently into each side of olfactory cleft, ensuring contact with the olfactory mucosa. Carriers will remain in place for a short duration to allow diffusion of PRP before dissolving naturally or being removed.

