## Primary Outcome:

- (1) Sniffin' Sticks Olfactory Test: Change in TDI score from baseline to 1 and 3 months post-intervention (with possible follow-up at 6 and 12 months).

Secondary Outcomes:

- (2)** Procedure evaluation: Record procedure time; assess pain via visual analogue scale (0–10) immediately post-procedure; document adverse events (e.g., persistent bleeding, infection) during procedure and within 2 weeks post-intervention.
- (3)** Sniffin' Sticks Parosmia Test: Assesses qualitative olfactory function in parosmia at baseline and 3-month follow-up.
- (4)** Montreal Cognitive Assessment (MoCA): Widely used to screen for mild cognitive impairment; olfactory loss may reduce sensory input to the brain, potentially impacting neural processing and cognitive function at baseline and 3-month follow-up.
- (5)** Visual Analogus Scale and Olfactory-Related Questionnaires: QOD, SNOT-22, PQ, subjective improvement ratings, 20-item retronasal olfactory test, SSParoT, procedure tolerability, and adverse event rates assessed pre-intervention and at 1 and 3 months (with possible follow-up at 6 and 12 months) post-intervention.
- (6)** Retronasal Olfactory Test: Uses standardized odorized powders/capsules in the oral cavity; participants exhale through the nose and rate the perceived odor; evaluates olfactory function via the retronasal route at pre-intervention and at 3 months post-intervention.
- (7)** Beck Depression Inventory (BDI): Standardized self-report tool assessing depressive symptom severity; olfactory loss from viral or other causes has been linked to mood disturbances and reduced emotional well-being.

Post-intervention care: All participants will continue standardized daily olfactory training for 12 weeks after PRP administration. Follow-up visits at 1 week, 1 month, and 3 months will assess smell function, symptom changes, and safety.

This study aims to determine whether carrier-assisted topical PRP application is as effective or superior to intranasal PRP injection for improving olfactory function, while potentially offering a less invasive and more tolerable treatment approach. Results will help define optimal PRP delivery strategies for olfactory rehabilitation in clinical practice.

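### Does a single-blind label that names no blinded party leave the primary TDI comparison unprotected?

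*Protocol*

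**What the plan says.** The only statement on blinding in the protocol text is in the Detailed Description: "This single-blind, randomized controlled trial will include a total of 60 adult patients aged 18-80 years old". Patient, operator, outcome assessor and analyst are not distinguished.

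The two arms are described just below it. For injection, "a 25-gauge needle will be used to deliver approximately 1 mL of PRP into multiple sites"; the preparation is given there as "After topical anesthesia with lidocaine spray and decongestion with oxymetazoline" and is not repeated for the other arm. For the carrier, "two pieces of PRP-soaked carrier will be placed gently into each side of olfactory cleft". Both procedures are intranasal and endoscopically guided. No sham injection or sham carrier is described.

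The primary outcome is "Change in TDI score from baseline to 1 and 3 months post-intervention". Item (5) of the secondary outcomes ends its list with "procedure tolerability, and adverse event rates assessed pre-intervention and at 1 and 3 months". The post-intervention care paragraph adds: "Follow-up visits at 1 week, 1 month, and 3 months will assess smell function, symptom changes, and safety". The protocol does not say who gives the TDI test.

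**The concern.** Single-blind has no fixed meaning, so a reader cannot tell from the label alone which safeguard is claimed. The operator cannot be blind to a needle or a sponge, and without a sham the patient is unlikely to be. That leaves the person who tests smell as the party whose blinding would protect the primary outcome, and the protocol describes no step that keeps the arm from that person.

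The schedule seems to add a route for unmasking. Tolerability and adverse events are listed at 1 and 3 months, the same time points as the primary TDI, and a patient asked how the procedure went could easily reveal which one it was. If the tester learned the arm, expectation could enter how the test is given and scored, and no analysis could remove it afterwards. The protocol also hopes that the carrier will prove gentler, so expectation is not an idle worry.

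**Working it through.** There is no figure to reproduce and no formula to apply. The check sets the statements side by side.

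**1. Who could be the blinded party?**

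| Party | What the protocol text allows | Would blinding this party protect the TDI? |
|---|---|---|
| Operator | Impossible: injects or places sponges | Not applicable |
| Patient | Unlikely, by inference: needle and sponge differ and no sham is described; the text does not say what patients are told | Yes, if it were achieved |
| Outcome assessor | Possible; nothing conflicts with it | Yes, in part, since the responses still come from the patient |
| Analyst | Possible | Not how the test is given |

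Assessor blinding is therefore the natural reading. It is not the only conceivable one, and the protocol does not say that patients will know their arm.

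**2. Does the schedule show that the assessor will be unmasked?**

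- The primary TDI is at 1 and 3 months. Item (5) names the same two months for tolerability and adverse events, an overlap of 2 of 2.
- Item (2) gives the specific timing: pain immediately after the procedure, and adverse events during it and in the following 2 weeks. That window closes before the 1-month TDI.
- Item (5) is a grouped list under one set of dates. Those dates include a pre-intervention assessment of procedure tolerability, which cannot exist before the procedure. The list also puts the retronasal test at 1 month, whereas item (6) has it only before the intervention and at 3 months. The dates in item (5) are thus a poor guide to what is collected when.
- The post-intervention care paragraph does place safety and smell function at the same visits. It gives neither an order nor a division of staff, so it does not show that the tester hears about the procedure before or during the test.

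The count of 2 of 2 is correct as a count of calendar months. It does not measure exposure to unmasking.

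**3. What about the patient-reported measures?**

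The questionnaires and ratings ("QOD, SNOT-22, PQ, subjective improvement ratings"), the pain scale and the BDI come from the patient. If patients know their arm, these are unblinded whoever else is masked, and naming the assessor as the blinded party would not alter that. One way of counting gives four tests that a masked assessor could protect (TDI, parosmia, retronasal, MoCA) and seven patient-reported measures (pain, QOD, SNOT-22, PQ, subjective improvement, tolerability, BDI). The split is not firm: participants themselves rate the odor in the retronasal test, and no reporter is named for tolerability. Neither number translates into a bias.

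**The case for a change.** The strongest case for a change is that who is masked, and who gives the test, is trial conduct. It is settled before the first visit and is not something a statistical analysis plan would supply. A label that names no party cannot be checked by a reader, and a site might apply it inconsistently. The remedy would be cheap: a sentence naming the party, a tester who did not attend the procedure, and smell tests before any questions about tolerability.

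Part of this stands. The blinded party is not named in the protocol text, and naming it would help a reader. If patients are not blinded, their own ratings should be read as unblinded.

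The rest does not carry a change. No rule, figure or analysis in the protocol is shown to be wrong, and the natural reading of the label already gives the protection sought. Directing the sponsor to declare the assessor as the blinded party would turn an inference into a protocol statement, and it would be untrue if another party was meant. The claim that existing staff could cover the separate roles has no support, because the text says nothing about staffing. Finally, the heading shows that the file also holds a consent form, a natural place to say who will know the arm. That form was not available here, so silence in the remaining text is weak evidence of omission.

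**Conclusion.** No change to the plan is called for. The protocol leaves a descriptive gap that a trial team can be expected to fill sensibly: two visibly different procedures under a single-blind label point to a masked outcome assessor, and on that reading the TDI comparison has the protection that this design can realistically offer. That protection is partial, because the patient's responses cannot be shielded from the patient's own knowledge of the procedure.

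The size of any bias is unknown and cannot be derived from the document. The overlap at both primary time points shows only that the visits coincide.

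The conclusion assumes that the site applies the label to the outcome assessor and that the TDI tester is kept away from the procedure and its records. It would need another look if the sponsor meant patient blinding, since no means of achieving that is described, or if the operator also gave the TDI test. The protocol text states neither.

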## Primary Outcome:

- (1) Sniffin' Sticks Olfactory Test: Change in TDI score from baseline to 1 and 3 months post-intervention (with possible follow-up at 6 and 12 months).

Secondary Outcomes:

- (2)** Procedure evaluation: Record procedure time; assess pain via visual analogue scale (0–10) immediately post-procedure; document adverse events (e.g., persistent bleeding, infection) during procedure and within 2 weeks post-intervention.
- (3)** Sniffin' Sticks Parosmia Test: Assesses qualitative olfactory function in parosmia at baseline and 3-month follow-up.
- (4)** Montreal Cognitive Assessment (MoCA): Widely used to screen for mild cognitive impairment; olfactory loss may reduce sensory input to the brain, potentially impacting neural processing and cognitive function at baseline and 3-month follow-up.
- (5)** Visual Analogus Scale and Olfactory-Related Questionnaires: QOD, SNOT-22, PQ, subjective improvement ratings, 20-item retronasal olfactory test, SSParoT, procedure tolerability, and adverse event rates assessed pre-intervention and at 1 and 3 months (with possible follow-up at 6 and 12 months) post-intervention.
- (6)** Retronasal Olfactory Test: Uses standardized odorized powders/capsules in the oral cavity; participants exhale through the nose and rate the perceived odor; evaluates olfactory function via the retronasal route at pre-intervention and at 3 months post-intervention.
- (7)** Beck Depression Inventory (BDI): Standardized self-report tool assessing depressive symptom severity; olfactory loss from viral or other causes has been linked to mood disturbances and reduced emotional well-being.

Post-intervention care: All participants will continue standardized daily olfactory training for 12 weeks after PRP administration. Follow-up visits at 1 week, 1 month, and 3 months will assess smell function, symptom changes, and safety.

This study aims to determine whether carrier-assisted topical PRP application is as effective or superior to intranasal PRP injection for improving olfactory function, while potentially offering a less invasive and more tolerable treatment approach. Results will help define optimal PRP delivery strategies for olfactory rehabilitation in clinical practice.

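### Procedure tolerability is scheduled once before the procedure and then not until 1 month, although a 1-week visit already exists

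*Protocol*

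**What the plan says.** The Protocol's outcome list (under the heading Primary Outcome, which also holds the Secondary Outcomes) deals with the procedure in two places.

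- **Item (2), Procedure evaluation:** "Record procedure time; assess pain via visual analogue scale (0–10) immediately post-procedure". Adverse events are documented "during procedure and within 2 weeks post-intervention".
- **Item (5), questionnaires:** at the end of a list of smell and quality-of-life instruments come "procedure tolerability, and adverse event rates assessed pre-intervention and at 1 and 3 months", with 6 and 12 months as possible extras.

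The post-intervention care paragraph sets the visits: "Follow-up visits at 1 week, 1 month, and 3 months will assess smell function, symptom changes, and safety". The primary outcome in item (1) is "Change in TDI score from baseline to 1 and 3 months post-intervention", so the 1- and 3-month times in item (5) are also TDI times.

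On the carrier arm, the Detailed Description says "Carriers will remain in place for a short duration to allow diffusion of PRP before dissolving naturally or being removed". It states the overall purpose as "Efficacy and safety of two PRP delivery methods will be compared", and the closing paragraph presents the carrier as a possibly gentler and better tolerated route.

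**The concern.** Tolerability and adverse event rates were placed in a list of repeated questionnaires and took on its schedule. That schedule suits an instrument with a meaningful baseline. It does not suit a rating of a single procedure: the first time falls before there is anything to rate, and the next is a month afterwards.

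The two arms differ in what the patient undergoes. One receives needle injections in a single session; the other has material placed in the olfactory cleft that may remain for a time after the session. One pain score at the end of the session describes the session only. If the arms differ in the discomfort that follows, the plan has no scale on which to show it until about a month later.

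Better tolerability is one of the stated hopes for the carrier. If the two methods prove similar on TDI, it would be a main reason to prefer one of them. A rating not taken at the time cannot be recovered later, so an analysis plan could not repair the gap.

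**Working it through.** The plan gives no figure to reproduce. The check sets the schedules side by side.

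| Time | Item (2) | Item (5), tolerability | Care paragraph |
|---|---|---|---|
| Pre-intervention | none | rating (void) | none |
| Procedure, day 0 | procedure time; pain VAS 0-10; adverse events | none | none |
| 1 week | within the 2-week adverse event window | none | visit: smell, symptoms, safety |
| 2 weeks | adverse event window ends | none | none |
| 1 month | none | rating | visit |
| 3 months | none | rating | visit |

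**Step 1. Usable times in item (5).** Fixed times: 3 (the possible 6 and 12 months are not counted). Before the procedure: 1. Usable: 3 − 1 = 2.

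**Step 2. When they fall.** With one month = 365.25/12 = 30.4 days, they fall at about day 30 and, since 3 × 30.4 = 91.3, about day 91. Both coincide with TDI assessments.

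**Step 3. Scores that bear on tolerability.** Adding the day-0 pain VAS gives 1 + 2 = 3 usable scores. None lies strictly between day 0 and about day 30, yet a visit at day 7 falls in that interval.

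**Step 4. What else is collected in the interval.** Adverse events are documented up to day 14, and symptom changes and safety are assessed at day 7. Both could record discomfort or blockage. Neither is named as a tolerability measure, and the text gives no scale for either that would allow an arm comparison of mild discomfort.

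**Step 5. What the change would do.** The first rating after day 0 moves from about day 30 to day 7. This is a calendar fact. The document offers nothing from which to work out how much recall over 30 rather than 7 days would shift a difference between arms.

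**The case against.** The strongest reply is that item (5) is loose drafting rather than a chosen tolerability schedule. It is one long list under one shared set of times. Subjective improvement ratings sit in it too and are equally impossible at baseline. The retronasal test also falls under the 1-month time there, although item (6) gives only pre-intervention and 3 months. On that reading, procedure-specific assessment belongs to item (2), and the times in item (5) are shorthand. This explains how the wording arose but does not close the gap: item (2) schedules no patient rating after the immediate pain score.

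Four stronger readings might be inferred, and the document does not support them.

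- **That discomfort after the session is captured only by recall a month later.** It is not. Adverse events are documented within 2 weeks, and symptoms and safety are assessed at 1 week. What is missing is a comparable rating.
- **That the adverse event windows in items (2) and (5) conflict.** They can be read as complementary: procedural events to 2 weeks, and rates reported at the later visits.
- **That the day-0 score is distorted by anaesthesia, or that carriers cause days of discomfort.** The injections follow topical lidocaine ("After topical anesthesia with lidocaine spray and decongestion with oxymetazoline, a 25-gauge needle will be used"), but no duration of action is given. Carriers stay for a short, unspecified time, and no dissolving time is stated. Both mechanisms are possible; neither is established.
- **That ratings at 1 and 3 months are coloured by whether smell has returned, to the advantage of one arm.** The coincidence with TDI visits is a fact; the bias and its direction are conjecture.

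It also stands that tolerability is a secondary matter here and appears in the aim only as a potential advantage.

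**Conclusion.** The point holds in a limited form. Item (5) fixes an impossible pre-intervention tolerability rating (1 of 3 fixed times), and no tolerability or discomfort rating is scheduled between the immediate pain VAS and about day 30, although patients attend at day 7. The early adverse event and symptom collection softens this but does not supply a measure on which the arms can be compared.

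The conclusion rests on reading item (5) as written and on the 1-week visit having no tolerability scale, since none is named. The size and direction of any effect on the comparison cannot be derived. The primary outcome and the power of the trial are not affected. Label: cheap improvement.

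**What to change.** Take procedure tolerability out of item (5), and with it the pre-intervention time. Add to item (2), in words such as:

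*Pain and nasal discomfort are each rated from 0 to 10, with the same wording in both arms, (a) immediately after the procedure and (b) at the 1-week visit, before smell testing, as the worst since the procedure.*

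A 1-month rating may be kept. Rating before smell testing keeps that day's test result from influencing the answer; it does not stop patients noticing their own sense of smell.

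**Cost.** No new visit. Two scales at two times make 2 × 2 = 4 fields, of which the day-0 pain score already exists, so 4 − 1 = 3 are new. Keeping a 1-month rating on both scales adds 2 more. The tolerability ratings now in item (5) fall away.

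**Downside.** The 1-week score still relies on up to 7 days of recall. If a carrier lasts beyond a week, discomfort after that visit is rated only if the 1-month rating is kept.

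### Does the missing assessment time for the Beck Depression Inventory, together with the double schedule for two smell tests, call for a change to the plan?

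*Protocol*

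**What the plan says.** Under Secondary Outcomes, item (7) reads "Beck Depression Inventory (BDI): Standardized self-report tool assessing depressive symptom severity" and ends with the rationale that "olfactory loss from viral or other causes has been linked to mood disturbances and reduced emotional well-being". It names no visit. The BDI is not in the timed list of item (5), and the sentence on visits after treatment does not name it: "Follow-up visits at 1 week, 1 month, and 3 months will assess smell function, symptom changes, and safety". The nearest comparable entry, item (4) on the Montreal Cognitive Assessment, also moves from description to rationale, but it finishes with a time: "potentially impacting neural processing and cognitive function at baseline and 3-month follow-up".

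Two smell tests appear twice. Item (3), the Sniffin' Sticks Parosmia Test, says "Assesses qualitative olfactory function in parosmia at baseline and 3-month follow-up". Item (6), the retronasal test, says it "evaluates olfactory function via the retronasal route at pre-intervention and at 3 months post-intervention". Item (5) opens with "Visual Analogus Scale and Olfactory-Related Questionnaires: QOD, SNOT-22, PQ, subjective improvement ratings" and continues with "20-item retronasal olfactory test, SSParoT, procedure tolerability, and adverse event rates assessed pre-intervention and at 1 and 3 months", adding possible follow-up at 6 and 12 months.

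**The concern.** A baseline score has to be taken before PRP is given and cannot be recovered later. If silence in item (7) meant that no baseline BDI would be collected, no patient's change in depressive symptoms could be reported. The arms would then be compared on follow-up scores alone, with less precision and no adjustment for chance imbalance in a 60-patient trial. With no follow-up time either, patients could be measured at different points, or a time could be chosen after the data were seen. An analysis plan can choose a model, but it cannot supply a score that was never taken, so the point cannot simply be left to an unseen SAP.

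The second part looks like a plain contradiction: one list schedules a 1-month parosmia and retronasal assessment and two other items do not.

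**Working it through.** **Stated times, side by side** (Protocol, Primary Outcome and Secondary Outcomes)

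| Item | Outcome | Times stated |
|---|---|---|
| (1) | TDI | baseline, 1 and 3 months; possibly 6 and 12 |
| (2) | Procedure evaluation | during and immediately after the procedure, and within 2 weeks |
| (3) | Parosmia test | baseline, 3 months |
| (4) | MoCA | baseline, 3 months |
| (5) | Scales and questionnaires, plus SSParoT and 20-item retronasal test | pre-intervention, 1 and 3 months; possibly 6 and 12 |
| (6) | Retronasal test | pre-intervention, 3 months |
| (7) | BDI | none |

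The factual part of the concern is therefore right: the BDI has no stated time. What does not follow is that no baseline is planned. A missing phrase in an entry that otherwise mirrors item (4) fits an omission better than a decision to skip the baseline.

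**Size of the BDI loss if no baseline were taken.** The Protocol gives no figure to reproduce here. The only input it supplies is 60 patients. Assumptions: 30 per arm, two-sided alpha 0.05, 80% power, and a baseline to 3-month correlation r of 0.3, 0.5 or 0.7.

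- Detectable difference from 3-month scores alone (two-sample t-test, 30 per arm): 0.736 SD.
- With baseline adjustment, multiply by √(1 − r²):
  - r = 0.3: 0.736 × √0.91 = 0.702 SD
  - r = 0.5: 0.736 × √0.75 = 0.637 SD
  - r = 0.7: 0.736 × √0.51 ≈ 0.53 SD
- Share of information lost without the baseline = r², which is 9%, 25% and 49%.
- In patients, 60 × r²: 60 × 0.09 = 5.4, 60 × 0.25 = 15.0 and 60 × 0.49 = 29.4.

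All of these figures depend on the baseline not being collected. If it is collected, the loss is 0. The effect thus runs from 0% to 49%, and its size is set by the unproven premise and an assumed correlation.

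**The two smell tests.** Suppose SSParoT is the Sniffin' Sticks Parosmia Test and the 20-item test is that of item (6). The names suggest this, though the Protocol does not define the abbreviation.

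- Both schedules contain baseline (or pre-intervention) and 3 months.
- They differ only at 1 month and at the optional 6 and 12 months.
- One-month assessments in doubt, before dropout: 60 × 1 = 60 if no patient takes SSParoT, up to 60 × 2 = 120 if all do.

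The timing phrase in item (5) is a blanket clause over a mixed list. That list includes procedure tolerability, which cannot be assessed before the procedure, so the phrase cannot be meant literally for every member.

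**The case for a change.** The strongest case for acting is that the times of a listed outcome belong in the protocol, that a missed baseline is irreversible, and that one clause in item (7) would remove the doubt at visits that already exist. The sentence on visits does not rescue the item: it concerns visits after treatment, and even if symptom changes were read to include mood, it would set no pre-treatment score.

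That much stands as a point about completeness of wording. What does not stand is the step from an unstated time to an absent assessment. Parts of the document are not at hand, so the safe statement is that the outcome list is silent, not that nothing is planned. An investigator who runs a MoCA at baseline and 3 months would most likely hand out a short self-report form at the same two visits. Even in the worst case, randomisation keeps a follow-up-only comparison of the arms unbiased; the cost is precision and the ability to report change, on the last-listed secondary outcome. The stated aim concerns olfactory function, invasiveness and tolerability, not mood.

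On the smell tests, one could settle the conflict by deleting both from item (5). That would give up 1-month and optional later results which the item says will be collected, in return for tidier text. Choosing the shorter schedule is a preference that the Protocol does not support.

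**Conclusion.** No change to the plan follows. The BDI entry lacks a time, which is a gap that the trial team would sensibly fill by following the pattern of item (4); writing the visits down completes the text and alters neither design nor analysis. The 9% to 49% loss of information applies only if no pre-treatment BDI is taken, with 30 per arm and r between 0.3 and 0.7 assumed; otherwise it is nil.

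The smell-test discrepancy is a real inconsistency of wording, provided the paired names denote the same instruments. It leaves 60 to 120 one-month assessments, and the optional later ones, uncertain. It does not touch baseline, the 3-month comparison or the primary TDI outcome. It is settled by giving each test one schedule when the visit plan is written out, without presuming the shorter one. Both points are clerical.
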